2.4 Secondary endpoints

2.4.1 Confirmatory secondary endpoints

The following two confirmatory endpoints will be tested for superiority of IDegLira vs. IDeg.

- Change from baseline in body weight after 26 weeks of treatment.
- Number of treatment emergent severe or BG confirmed hypoglycaemic episodes during 26 weeks of treatment.

The tests for superiority of the confirmatory secondary endpoints will be based on the FAS and will only be carried out if non-inferiority of IDegLira vs. IDeg and superiority of IDegLira vs. liraglutide with regards to the primary endpoint are confirmed.

In order to control the overall type I error on a 2-sided 5% level with regards to the secondary endpoints, a hierarchical testing procedure will be used. If superiority is confirmed with respect to change from baseline in body weight after 26 weeks of treatment the number of treatment emergent severe or BG confirmed hypoglycaemic episodes during 26 weeks of treatment will be tested for superiority.

Superiority for change from baseline in body weight will be considered confirmed if the upper bound of the two-sided 95% confidence interval for the estimated mean treatment difference (IDegLira minus IDeg) is strictly below zero or equivalently if the p-value for the one-sided test of

$$H_0 D \geq 0.0 \text{ against } H_A D < 0.0,$$

is less than 2.5%, where D is the treatment difference.

The change from baseline in body weight after 26 weeks of treatment will be analysed using an ANCOVA model with treatment and previous OAD treatment (metformin ± one other OAD) as fixed factors and baseline weight as covariate.

Similar sensitivity analyses as specified for the primary endpoint (ANCOVA on the PP analysis set and CAS; MMRM; the pattern mixture model similar to that described for HbA_{1c}, but without added non-inferiority penalty) will be performed.

Superiority for hypoglycaemic episodes will be considered confirmed if the upper bound of the two-sided 95% confidence interval for the estimated mean treatment ratio (IDegLira vs. IDeg) is strictly below one or equivalently if the p-value for the one-sided test of

$$H_0 \text{ RR} \geq 1.0 \text{ against } H_A \text{ RR} < 1.0,$$

is less than 2.5%, where RR is the treatment rate ratio.

Number of treatment emergent severe or BG confirmed hypoglycaemic episodes during 26 weeks of treatment will be analysed using a negative binominal regression model with a log-link function and the logarithm of the time period in which a hypoglycaemic episode is considered treatment emergent as offset. The model will include treatment and previous OAD treatment as fixed factors.

As a sensitivity analysis, for withdrawn subjects, the number of episodes in the missing period (time of withdrawal to planned treatment emergent period [max of 27 weeks and longest treatment emergent time observed in the trial, in all 3 treatment arms]) will be imputed using a multiple imputation technique⁴. The first step (getting samples from the posterior distribution) is done once, for all three arms together. In the second step, the imputation will follow the hypothesis being tested. When deriving the IDegLira vs. IDeg treatment ratio the imputation will be based on an assumption that the event rates before and after withdrawal in both arms correspond to the event rate in the IDeg group. Similarly for the IDegLira vs liraglutide treatment ratio, the event rate before and after withdrawal is assumed to correspond to the event rate in the liraglutide arm. In other words: two imputation datasets will be made, one for IDegLira and IDeg and one for IDegLira and liraglutide. In the analyses, depending on the hypothesis being tested, the respective imputation dataset will be used and the third arm (from the other imputation dataset) will be kept in the model.

The imputation will be done as follows:

- As a first step, a Bayes negative binomial model with the same fixed factors used in the original confirmatory analysis model is fitted to the event rate data to obtain the posterior distribution of model parameters.

- In the second step, based on the estimated parameters for comparator in this model, the number of events in the missing period is imputed for all withdrawn subjects, i.e. pre and post withdrawal event rates in the conditional distribution used for imputation are as for a given comparator. Multiple copies (1000 copies) of a complete data set are generated by sampling from the estimated distribution.

For each of the complete data sets, the number of events is analysed using a negative binomial model including the same fixed factors used in the original model.

The estimates and standard deviations for the 1000 data sets are pooled to one estimate and associated standard deviation using Rubin's rule³. From these pooled estimates the confidence interval for the treatment ratio and the associated p-value are calculated.

Subjects with missing exposure time will not contribute to the analysis.

2.4.2 Supportive secondary endpoints

2.4.2.1 Efficacy endpoints

In the following the statistical models will be fitted to all data simultaneously (all treatment groups) and from this model the treatment differences for IDegLira vs. IDeg and IDegLira vs. liraglutide will be estimated. For insulin dose, the model will be fitted only to data from the IDegLira and IDeg treatment groups.

Insulin dose after 26 weeks of treatment

The actual daily insulin dose after 26 weeks of treatment will be analysed using an ANCOVA model including treatment and previous OAD treatment as fixed factors and baseline HbA_{1c} value as covariate.

Responder for HbA_{1c} after 26 weeks of treatment

Two dichotomous endpoints (responder/non-responder) will be defined based on whether a subject has met a specific target level after 26 weeks of treatment:

- ADA HbA_{1c} target (HbA_{1c} < 7.0%)
- International Diabetes Federation (IDF) HbA_{1c} target (HbA_{1c} ≤ 6.5%)

Analysis of each of the two responder endpoints will be based on a logistic regression model with treatment and previous OAD treatment as fixed factors and baseline HbA_{1c} value as a covariate.

HbA_{1c} responder endpoints without weight gain

Responder for HbA_{1c} without weight gain after 26 weeks of treatment will be defined as HbA_{1c} < 7.0% or ≤ 6.5% at end of treatment and change from baseline in body weight below or

equal to zero. Analysis of each of the two responder endpoints will be based on a logistic regression model with treatment and previous OAD treatment as fixed factors and baseline HbA_{1c} and body weight values as covariates.

HbA_{1c} responder endpoints without hypoglycaemic episodes

Responder for HbA_{1c} without hypoglycaemic episodes after 26 weeks of treatment will be defined as HbA_{1c} < 7.0% or ≤ 6.5% at end of treatment and without severe or BG confirmed episodes during the last 12 weeks of treatment. Analysis of each of the two responder endpoints will be based on a logistic regression model with treatment and previous OAD treatment as fixed factors and baseline HbA_{1c} values as a covariate.

HbA_{1c} responder endpoints without hypoglycaemic episodes and weight gain

Responder for HbA_{1c} without hypoglycaemic episodes and weight gain after 26 weeks of treatment will be defined as HbA_{1c} < 7.0% or ≤ 6.5% at end of treatment, without severe or BG confirmed episodes during the last 12 weeks of treatment, and change from baseline in body weight below or equal to zero. Analysis of each of the two responder endpoints will be based on a logistic regression model with treatment and previous OAD treatment as fixed factors and baseline HbA_{1c} and body weight values as covariates.

Fasting plasma glucose (FPG)

Change from baseline in FPG after 26 weeks of treatment will be analysed using the standard ANCOVA model.

Waist circumference

Change from baseline in waist circumference after 26 weeks of treatment will be analysed using the standard ANCOVA model.

Beta-cell function (fasting insulin, fasting C-peptide, fasting glucagon, and HOMA-β)

In addition to fasting insulin, fasting C-peptide, and fasting glucagon, one derived parameter will be calculated; beta-cell function (HOMA-β). The calculation of the HOMA endpoint will be done as follows:

- Beta-cell function (%) = $20 \cdot \text{fasting insulin}[\mu\text{U/mL}] / (\text{FPG}[\text{mmol/L}] - 3.5)$

These endpoints after 26 weeks of treatment will be analysed separately using the standard ANCOVA model. In these statistical analyses the endpoint will be log-transformed and so will the baseline covariate.

Fasting lipid profile

Cholesterol, LDL cholesterol, HDL cholesterol, VLDL cholesterol, triglycerides, and free fatty acids after 26 weeks of treatment will be analysed separately using the standard ANCOVA model. In these statistical analyses the endpoint will be log-transformed and so will the baseline covariate.

Self-measured plasma glucose 9-point profile

Three endpoints from the 9-point profile will be defined:

- 9-point profile
- Mean of the 9-point profile, defined as the area under the profile (calculated using the trapezoidal method) divided by the measurement time
- Post-prandial plasma glucose increments (from before meal to 90 min after for breakfast, lunch and dinner). The mean increment over all meals will be derived as the mean of all available meal increments

A mixed effect model will be fitted to the 9-point profile data. The model will include treatment, previous OAD treatment, time, interaction between treatment and time, and interaction between previous OAD treatment and time as fixed factors, and subject as random effect, where measurements within subjects will be assumed correlated with a compound symmetry covariance matrix. From the model mean profile by treatment and relevant treatment differences will be estimated and explored.

Change from baseline after 26 weeks of treatment in mean of the 9-point profile and post-prandial increment endpoints will be analysed separately using the standard ANCOVA model.

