1.2 Scope of the statistical analysis plan

This Statistical Analysis Plan (SAP) is based on final Protocol version 5.0 (05-Dec-2016). The scope of this SAP is to add one sensitivity analysis for change from baseline in HbA_{1c} after 26 weeks of treatment and several sensitivity analyses for confirmatory secondary endpoints, and to perform other minor changes. For further details on the changes see section [3](#).

2 Statistical considerations

Novo Nordisk will analyse and report data from all sites together.

All analyses of efficacy and safety endpoints will be based on the full analysis set (FAS). The analysis of the primary endpoint and the confirmatory secondary endpoint, change from baseline in body weight after 26 weeks of treatment, will be repeated on the per-protocol (PP) analysis set and the completer analysis set (CAS) for sensitivity purposes. All efficacy endpoints will be summarised using the FAS and safety endpoints will be summarised using the safety analysis set (SAS).

The impact of protocol deviations and outliers may be investigated further in sensitivity analyses if deemed relevant.

Unless otherwise specified, all continuous measurements will be summarised descriptively at each visit by treatment using observed data. After 26 weeks of treatment, descriptive statistics will be presented based both on observed and last observation carried forward (LOCF) imputed data. Endpoints that are analysed untransformed and endpoints that are not formally analysed are summarised by the arithmetic mean, standard deviation (SD), median, and minimum and maximum value. Endpoints that are analysed log-transformed are summarised by the geometric mean and coefficient of variation (CV).

For measurements over time, mean values will be plotted to explore the trajectory over time. LOCF imputed data will be used as the basis for plotting data, if not otherwise specified. For endpoints that are analysed log-transformed, the geometric mean values will be plotted.

A standard analysis of covariance (ANCOVA) model will be applied for the continuous primary and secondary endpoints. The model includes treatment and previous OAD treatment (metformin or metformin in combination with one other OAD) as fixed factors and the corresponding baseline value as covariate. In the following, this model will be referred to as the standard ANCOVA model.

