2.5 Pharmacokinetic modelling

Population pharmacokinetic analysis

The objective for this analysis is to compare the pharmacokinetics of IDegLira and its individual components at clinically relevant doses during 26 weeks of treatment. Furthermore, dose-proportionality of IDeg and liraglutide exposures following doses of IDegLira will be evaluated and the effects of pre-specified covariates on exposures of IDeg and liraglutide will be investigated. Pharmacokinetic samples for IDeg and liraglutide sampled at site visits will be included in the analysis. No pre-defined time of day is specified for the sampling, but the date and exact clock time of sampling will be recorded by the investigator. The subjects must be instructed to write in their

diary the date, exact clock time, dose, and injection site of the previous three days of dosing as well as the dose on the day of the visit, if taken before PK blood sampling.

The population PK analysis will be performed by the Quantitative Clinical Pharmacology Department at Novo Nordisk. A more technical and detailed elaboration of the population PK analysis will be given in the modelling analysis plan (MAP) which will be finalised before DBL.

The pre-specified analysis will explore the effects of covariates on the IDeg and liraglutide exposure. The structural models and covariate relationships will be predefined in detail in the MAP. In brief, previously developed population PK models for IDeg and liraglutide will be used. For both PK models, the absorption rate constant (K_a) will be fixed and the apparent clearance (CL/F) and the apparent volume of distribution (V_d/F) will be estimated.

The covariates of interest will be evaluated using criteria which will be specified in the MAP.

The following covariates will be tested on the apparent clearance (CL/F):

- Dose
- Treatment (IDegLira, IDeg, liraglutide)
- Injection site area (Abdomen, Upper arm, Thigh)
- Body weight
- Age group (< 65 , ≥ 65 years)
- Gender (Male/Female)

For the categorical variables, it is a requirement to have at least 20 subjects in each category.

Exposure-response analysis

The exposure-response relationship will be investigated for selected response variables, such as HbA_{1c} . Individual drug concentration data will be tabulated in the CTR.

The population PK and exposure-response analyses will be reported in a separate modelling report, which will not be a part of the CTR.

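### The supportive insulin-dose ANCOVA uses baseline HbA1c as its only covariate; adding baseline body weight, which is already collected, might gain some precision

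*SAP*

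**What the plan says.** Insulin dose falls under "2.4.2 Supportive secondary endpoints". Section 2.4.2.1 of the SAP specifies that "daily insulin dose after 26 weeks of treatment will be analysed using an ANCOVA model including treatment and previous OAD treatment as fixed factors", followed by baseline HbA1c "value as covariate". It also says: "For insulin dose, the model will be fitted only to data from the IDegLira and IDeg treatment groups". The endpoint is the absolute daily dose.

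The general rule in section 2 (Statistical considerations) is a standard ANCOVA with treatment and previous OAD "as fixed factors and the corresponding baseline value as covariate". The dose endpoint cannot follow that rule. Section 1.1 describes a population on metformin with or without one other oral drug, so no corresponding baseline dose exists, and the SAP substitutes baseline HbA1c.

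Baseline weight is collected and modelled elsewhere. The confirmatory body-weight analysis in section 2.4.1 has treatment and previous OAD "as fixed factors and baseline weight as covariate".

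Output 1 of the attached statistical documentation fits exactly the dose model that section 2.4.2.1 describes.

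**The concern.** With no baseline dose available, the choice of substitute covariate is open, and the SAP gives no reason for stopping at HbA1c. In output 1 the chosen adjusters do little: the residual SD is still about 12.5 units, against adjusted means of 24.6 and 30.1 units. Because the dose is not scaled by body size, baseline weight is a natural candidate for absorbing some of that spread.

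Only the width of one supportive interval is at stake, together with protection of that comparison against a chance weight difference between the arms. In a linear model without interactions, adding a baseline covariate leaves the treatment effect being estimated unchanged.

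**Working it through.** **Inputs.**
- Output 1 (dose): residual variance 156.79; 530 of 540 observations used; 526 residual df; baseline HbA1c t = 3.84; previous OAD t = −0.69; adjusted means 24.6139 (SE 0.6640) for IDegLira and 30.1057 (SE 0.9504) for IDeg; contrast −5.4917 (SE 1.1603), 95% CI −7.7712 to −3.2123.
- Output 12 (body weight): residual variance 6.8139; SE of the baseline-weight slope 0.007083; 720 of 720 observations used; IDegLira adjusted mean 74.2782 kg and adjusted change 0.1480 kg.
- Partial correlation r of dose with baseline weight: not documented. Assumed range 0 to 0.5.

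**1. Reproduce the reported precision.** Effective arm sizes from the SEs of the adjusted means are 156.79/0.6640² = 355.6 and 156.79/0.9504² = 173.6. Then SE = √[156.79 × (1/355.6 + 1/173.6)] = 1.159, against 1.1603 reported. The interval −5.4917 ± t(0.975, 526) × 1.1603 gives −7.771 to −3.212, which agrees.

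**2. What the present covariates explain.** Partial R² = t²/(t² + 526). For baseline HbA1c, 3.84²/(3.84² + 526) = 0.027, so r is about 0.16. For previous OAD, 0.69²/(0.69² + 526) = 0.0009.

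**3. Spread of baseline weight.** The SE of the slope satisfies SE² = residual variance / Sxx. Here Sxx is the sum of squares of baseline weight within treatment and OAD groups, on 720 − 4 = 716 df. So the SD is √(6.8139/0.007083²/716) = 13.77 kg. The mean is 74.2782 − 0.1480 = 74.13 kg.

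**4. A benchmark from the documents' figures.** The mean dose over the two arms is (24.6139 × 355.6 + 30.1057 × 173.6)/529.2 = 26.4 units. If dose were strictly proportional to weight, the slope would be 26.4/74.13 = 0.356 units/kg. Weight would then explain (0.356 × 13.77)² ≈ 24.1 of the 156.79, so R² ≈ 0.154 and r ≈ 0.39. Proportionality is an assumption made for scale; the documents do not state it.

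**5. SE with weight added.** SE_new = 1.1603 × √[(1 − r²) × 526/525], holding the point estimate at −5.4917:

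| r (r²) | SE | Change | 95% CI | t |
|---|---|---|---|---|
| 0 (0) | 1.161 | +0.1% | −7.77 to −3.21 | −4.73 |
| 0.16 (0.027), as strong as HbA1c | 1.146 | −1.3% | −7.74 to −3.24 | −4.79 |
| 0.32 (0.10) | 1.102 | −5.0% | −7.66 to −3.33 | −4.98 |
| 0.39 (0.154), proportional dose | 1.069 | −7.9% | −7.59 to −3.39 | −5.14 |
| 0.50 (0.25) | 1.006 | −13.3% | −7.47 to −3.52 | −5.46 |

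**6. Chance imbalance.** The SE of the weight difference between the arms is 13.77 × √(1/355.6 + 1/173.6) ≈ 1.27 kg. Under the proportional benchmark, an imbalance of that size would shift the contrast by 0.356 × 1.27 ≈ 0.45 units. The material at hand gives no baseline weights by arm, so this is the size to expect from chance and not an observed imbalance.

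**The case against.** The strongest answer is that nothing here is wrong. The model is fully specified and was fitted as written. Leaving a prognostic covariate out of a randomised linear comparison causes no bias. The endpoint lies outside the testing hierarchy and the sample-size calculation, and the planned model already gives t = −4.73. The benefit could also be nil, because the one baseline covariate whose relation to dose is strong enough to register, HbA1c, reaches a partial correlation of only about 0.16. All of this stands, and it limits the point to an optional improvement.

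A reader might also infer that the SAP contradicts itself. Section 2.5 names body weight on its list ("The following covariates will be tested on the apparent clearance (CL/F") and some responder models use "baseline HbA_{1c} and body weight values as covariates". Neither supports that inference:
- The pharmacokinetic list names covariates to be tested on clearance, in a modelling report outside the clinical trial report. It does not say that weight predicts the dose reached by titration. It also contains age group, gender and injection site, so as an argument it would prove too much.
- The responder models include weight only where absence of weight gain is part of the endpoint. The other HbA1c responder models adjust for baseline HbA1c alone.

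Nor does the SAP give the dose comparison any special rank among the supportive endpoints.

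The objection does not remove the asymmetry of cost: the possible loss is one degree of freedom in 526, against a possible gain of several per cent in the SE.

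**Conclusion.** The point holds as a minor, optional improvement. The dose model relies on one weak substitute covariate and omits a baseline value that is already collected, so precision may be left unused. It would be too strong to say that precision is lost, because that depends on a dose–weight correlation the documents do not report.

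Over partial correlations from 0 to 0.5, the SE of 1.1603 runs from 0.1% larger to about 13% smaller. The proportional-dose benchmark gives about 8% smaller. These figures assume a linear weight effect common to both arms and an unchanged point estimate. The 13.8 kg SD comes from all three arms, whereas the dose model uses two. Neither this comparison nor any confirmatory conclusion would change.

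**What to change.** In a plan still open to change, word the insulin-dose model as: *treatment and previous OAD treatment as fixed factors, with baseline HbA1c and baseline body weight as covariates*. This costs one phrase and one model term. The body-weight ANCOVA used all 720 subjects, so missing baseline weights should cost no observations.

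For this trial the prespecified result is already attached. Keep that model as the reported analysis and show the weight-adjusted fit beside it, labelled as a post hoc sensitivity analysis. It should not be presented as a correction. One rerun of output 1 would also supply the missing dose–weight correlation and settle the size of the gain.
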